### 9.3 Vital Signs and Weight

Subjects will be monitored before, during and after tremelimumab and durvalumab infusion with assessment of vital signs as presented in section 6.5 of the protocol.

- Descriptive statistics will be presented each timepoint.
- Descriptive statistics will also be presented for the changes in vital signs from baseline to each post-treatment assessment time point.

### 9.4 Electrocardiograms

12-Lead ECG will be completed at screening/baseline visit, Day 1 of cycles 1, 2, 4, 6, 8, 10 and 12 and the +28 day post last treatment visit.

- Baseline and post-baseline assessments will be classified as normal, abnormal – not clinically significant, or abnormal – clinically significant. The baseline value will be the pre-dose assessment for each formulation, and the post-baseline value will be the worst post-baseline assessment for each formulation.

- ECG data will be presented in a data listing.

### 9.5 ECOG Performance

ECOG performance will be evaluated on a 6-point scale from grade 0-5. ECOG PS assessments will be summarized overall by time point utilizing descriptive statistics. ECOG performance status will be taken except on Cycle 2 Day 8, Cycle 4 Day 8, Cycle 7 Day 22, Cycle 12 Day 8, and the post study follow-up.

- ECOG PS assessments will also be summarized as categorical variable by timepoint with the n and percentage being displayed for each arm or indication-specific cohort.

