### 3.1.10 Subject Withdrawal from Treatment or from Study

A subject will be **withdrawn from study treatment** for any of the following reasons:

1. Withdrawal of consent for further treatment
2. Pregnancy or intent to become pregnant
3. DLT at any time (see Section 3.1.9)
4. Progressive disease requiring alternative systemic treatment
5. Significant protocol violation or noncompliance that, in the opinion of the Investigator or Sponsor, warrants withdrawal
6. Development of intercurrent, non-cancer-related illnesses or complications that prevent either continuation of therapy or regular follow-up
7. Best medical interest of the subject (at the discretion of the Investigator)

Discontinuation from receiving study treatment does not mean that the subject is withdrawn from the study. If applicable, subjects who are withdrawn from study treatment should undergo the planned On Study Follow-up procedures (see Study Flowchart, Section 3.2), followed by the Post Study follow-up period (see Section 3.1.16).

A subject will be **withdrawn from the study** for the following reasons:

1. Best medical interest of the subject at the discretion of the Investigator
2. Initiation of alternative anticancer therapy (marketed or investigational)
3. Withdrawal of consent for all follow-up
4. Lost to follow-up
5. Death

Section 7.2.6 provides additional details regarding documentation for early subject withdrawal from study treatment and early withdrawal from study.

See also Sections 8.3 and 8.4 for subject withdrawal from treatment due to necessary dosing interruptions or discontinuations.

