### **3.1.10.1 Treatment beyond Progression**

Subjects meeting criteria for progression by irRECIST (Section 8.5) will be allowed to continue on therapy until confirmation of progression by irRECIST if the subject agrees and signs an appropriate informed consent form regarding continuation of treatment and as long as the following criteria are met at the discretion of the Investigator:

- a. Absence of symptoms and signs (including worsening of laboratory values) indicating disease progression;
- b. No significant decline in ECOG performance status;
- c. Absence of rapid progression of disease or of progressive tumor at critical anatomical sites (e.g., cord compression) requiring urgent alternative medical intervention.

See Section 8.5 for additional information regarding RECIST 1.1 and irRECIST.

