## 2.2 Study Endpoints

### Primary Endpoints

The primary endpoint of the combination therapy of durvalumab and tremelimumab are:

- Dose- Limiting Toxicities (DLTs). DLTs are defined as any adverse events that are possibly, probably, or definitely related to the administration of durvalumab, tremelimumab, or BI 1361849 components. This applies to Dose Evaluation subjects during the DLT Evaluation period.
- Safety and tolerability evaluated using CTCAE 4.03.
- Recommended Combination Dose (RCD) determined in Dose Evaluation Phase.

The safety endpoints for this study include:

[figure not shown]
- Treatment-emergent adverse events (TEAEs) and serious AEs (SAEs)
- Clinical laboratory tests (hematology and chemistry)
- Vital signs and weight measurements
- ECG
- ECOG performance status evaluation
- Any other medically indicated assessments, including subject interviews
- All safety analyses will be reported separately for Arm A and Arm B

The Clinical efficacy endpoints will be assessed by irRECIST and RECIST 1.1 and will include:

- Objective Response rate (ORR) at 8 and 24 weeks. ORR is defined as the percentage of subjects meeting criteria of Complete Response (CR) or Partial Response (PR) over a period of at least 4 weeks.
- Duration of Response (DoR). DoR is defined as the interval between the date of earliest determination of CR or PR to the date of earliest determination of PD, or to the date of death, if PD does not occur.
- Disease Control rate (DCR). DCR is defined as the percentage of subjects meeting criteria of Stable Disease (SD), PR, or CR over a period of at least 4 weeks.
- Progressive Free Survival (PFS) at 8 and 24 weeks. PFS is defined as the interval between the date of first dose to the date of earliest determination of Progressive Disease

(PD), or to the date of death, if PD does not occur. Week 8 corresponds to Cycle 3 Day 1 and Week 24 corresponds to Cycle 7 Day 1.

- Overall Survival (OS). OS is defined as the interval between the date of first dose until the date of death or the date of last follow-up.
- All efficacy analyses will be reported separately for Arm A and Arm B.

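### SAP 9.5 summarises ECOG status only by time point, with no comparison to each subject's baseline and no rule for deaths or missed assessments, so the tables cannot show how many treated subjects worsened

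*SAP*

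**What the plan says.** SAP 2.2 includes "ECOG performance status evaluation" among the safety endpoints, and safety and tolerability is the primary objective. SAP 9.5 sets the scale, "ECOG performance will be evaluated on a 6-point scale from grade 0-5", and then plans two displays. The first: "ECOG PS assessments will be summarized overall by time point utilizing descriptive statistics". The second: "ECOG PS assessments will also be summarized as categorical variable by timepoint with the n and percentage being displayed", by arm or cohort. Neither has a stated denominator. SAP 11.1 allows for replacement of subjects, listings of data as collected and imputation of partial dates. It has nothing on missing ECOG assessments.

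In the protocol, inclusion criterion 6 admits ECOG up to 2, and Section 8.7 defines grade 5 as death. The flowchart (Section 3.2) places ECOG in the physical examination row, which is marked at the treatment visits and at +28, +42 and +91 days after the last dose.

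**The concern.** The safety question for this endpoint is how many of the treated subjects got worse, and by how much. A by-time-point table gives the distribution of grades among those assessed at that visit. The two differ in two ways.

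First, a subject at ECOG 2 in a later column may have entered at 2 or fallen to 2, and the table does not say which. Second, subjects leave treatment for progression, toxicity or intercurrent illness, or die, so who remains in a late column is related to how subjects are doing. With about 20 subjects per arm, a late column can look reassuring because of who is no longer in it. A reader of the study report could then take a stable ECOG profile as evidence of tolerability when the table cannot support that.

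**Working it through.** The plan gives no figure to reproduce here. The check is a comparison of sections, followed by an illustration of how thin the late columns could be.

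**1. What each safety section plans within subject**

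| SAP section | Comparison with baseline |
|---|---|
| 9.2 Laboratory data | change from baseline, and low/normal/high shift tables for most analytes |
| 9.3 Vital signs | change from baseline to each time point |
| 9.4 ECG | baseline and worst post-baseline classified: "the post-baseline value will be the worst post-baseline assessment for each formulation" |
| 9.6 Physical examination | clinically significant changes from baseline |
| 9.5 ECOG | none |

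Section 9.6 covers the flowchart row that contains ECOG, but does not name ECOG. The ECG contrast should not be pressed, because the only output 9.4 specifies is a listing. The laboratory and vital-sign sections are the firm comparators.

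**2. Why by-visit counts cannot give the number who worsened**

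Take two subjects, one entering at ECOG 1 and one at ECOG 2. If neither changes, the later column shows one subject at each grade. If the first falls to 2 and the second improves to 1, the column is identical, yet one subject has worsened. No attrition is needed for this.

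**3. Deaths and missed assessments**

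The scale runs to grade 5, which is death, but no rule puts a deceased subject into any ECOG column. With no denominator and no missing-data rule, the natural reading is that percentages use whoever was assessed. That is an inference; the mock shells mentioned in SAP 13.0 may settle it.

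**4. How many could be in the late on-treatment columns (illustration only)**

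Inputs: 20 subjects per arm at the RCD (Protocol 3.1.7.2). Elapsed days come from the flowchart study days: Week 9 = 57 − 1 = 56, Week 17 = 113 − 1 = 112, Week 25 = 169 − 1 = 168, Week 45 = 309 − 1 = 308. Assumption: time on treatment is exponential with median m months. The central m is 2.9, the median PFS of the earlier vaccine trial (Protocol 1.2.3); the range is 2 to 6.

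Formula: expected number on treatment = 20 × 0.5^(t/m), with t = days/30.4375.

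Worked case, Week 25: t = 168/30.4375 = 5.52 months; 5.52/2.9 = 1.90; 0.5^1.90 = 0.267; 20 × 0.267 = 5.3.

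| Visit | m = 2 | m = 2.9 | m = 6 |
|---|---|---|---|
| Week 9 | 10.6 | 12.9 | 16.2 |
| Week 17 | 5.6 | 8.3 | 13.1 |
| Week 25 | 3.0 | 5.3 | 10.6 |
| Week 45 | 0.6 | 1.8 | 6.2 |

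**5. What the follow-up visits add**

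SAP 9.5 excludes only four named treatment-period visits and the post-study follow-up, so the +28, +42 and +91-day values are tabulated. They are timed from the last dose, so each column pools early and late stoppers, and no display ties them to the subject's baseline.

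**The case against.** The strongest case against has four parts.

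- **Removal of decliners.** A reader might infer that the protocol takes subjects off treatment when ECOG falls. It does not. The criterion "No significant decline in ECOG performance status" is one of three conditions, judged by the investigator, in a permissive rule for subjects who have already progressed: "Subjects meeting criteria for progression by irRECIST (Section 8.5) will be allowed to continue on therapy until confirmation of progression by irRECIST". The withdrawal list in Protocol 3.1.10 does not name ECOG. The nearest item is "Best medical interest of the subject (at the discretion of the Investigator").
- **Only the fittest are seen.** This inference also goes too far. Stopping treatment is not leaving the study (3.1.10). Subjects who stop enter a 90-day follow-up with three visits (3.1.16), and an End of Study visit is required on study withdrawal (3.1.16.1). Many who deteriorated should therefore appear in a follow-up column. Those who die or do not attend are the ones lost.
- **Other outputs.** Protocol 4.1.1 sends clinically significant deteriorations, including those found by ECOG evaluation, to the adverse event record. SAP 9.1.1 tabulates events by maximum severity and counts deaths, and OS captures death again.
- **Size and use.** The 2.9-month figure is PFS from a different regimen and setting. It is a loose proxy for time on treatment here, since treatment past progression is possible. The documents give no share of leavers whose ECOG had declined, so any estimate of hidden decliners is unsupported. The arms are non-randomised and reported separately, so no planned between-arm comparison is spoiled.

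All four limit the point, and none removes it. Adverse event tables are organised by system organ class and preferred term, not by ECOG grade change, and include only what was judged clinically significant. Deaths are counted elsewhere. No planned output combines these into a per-subject ECOG result.

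**Conclusion.** The point holds as a gap in a descriptive display. For a listed safety endpoint, SAP 9.5 offers no within-subject comparison and no treatment of deaths or missing assessments, so the number of treated subjects who worsened cannot be read from the ECOG tables. That conclusion rests on the text of 9.5 and the entry range of 0 to 2, and needs no attrition assumption.

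The secondary point, that late on-treatment columns describe a small and selected group, depends on how fast subjects stop. Under the assumptions shown, roughly 5 of 20 (3 to 11) would remain on treatment at Week 25 and 2 (1 to 6) at Week 45. These are illustrations. The documents do not support a numerical bias, or a claim that ECOG will look stable or improve. DLT assessment and RCD selection do not use these tables. This is a cheap improvement to reporting.

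**What to change.** In SAP 9.5:

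- Add, by arm on all treated subjects (the ITT population of SAP 4.1), a shift table from baseline ECOG to worst post-baseline ECOG through the +91-day On Study Follow-up visit.
- Report the number and percent worsening by 1 or more grades and by 2 or more grades.
- Show deaths in that period, and subjects with no post-baseline assessment, as separate rows. Scoring death as grade 5 is debatable, because it would mix deaths from disease with tolerability; a separate row avoids that choice.
- In the by-visit table, state the denominator and show the numbers assessed, died and not assessed out of all treated subjects.

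The cost is one added descriptive table and a few rows in an existing one. It uses data already scheduled for collection and needs no new visits or assessments.

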### 9.6 Physical Examinations

A full physical examination will be performed at screening/baseline. There will also be targeted physical examinations at other timepoints except on Cycle 2 Day 8, Cycle 4 Day 8, Cycle 7 Day 22, Cycle 12 Day

8, and the post study follow-up.

- Continuous and categorical variables at baseline and various timepoints will be summarized using descriptive statistics.
- Clinically significant changes from baseline to postbaseline time points will be summarized using descriptive statistics.

### 9.7 Pregnancy Testing

Serum pregnancy testing (when applicable) is required prior to dosing up to 1 week before start of treatment. Pregnancy testing is also done on Day 1 of Cycles 1, 3, 5, 7, 9, 11, and On Study Follow-up Days +28 and +91 Days. Also, all subjects of childbearing potential who withdraw from study must have a serum pregnancy test done at the End of Study visit, unless it was done within 7 days prior to the End of Study Visit.

- The results of pregnancy testing (Yes/No) will be summarized for every applicable timepoint with the n and percentage being displayed for each arm or cohort.

## 10.0 EXPLORATORY ANALYSIS

Per Protocol Amendment 9.1, some of the biological assessment tests will no longer be applicable. Hence, some blood sample collections for immune monitoring were discontinued as indicated in the study flow chart.

## 11.0 STATISTICAL/ANALYTICAL ISSUES

### 11.1 Handling of Dropouts or Missing Data

In the dose evaluation phase, subjects who are not fully evaluable for DLT per section 4.1.2 of the protocol may be replaced.

Subjects who are not fully evaluable for the PFS rate and ORR may be replaced.

All available data will be presented on the data listings as collected.

Algorithms for imputing partial or missing dates related to AEs and prior/concomitant medications are shown below in Table 4.

**Table 4 Imputation Rules for Partially Missing Dates**

Variable	Missing Day	Missing Day, Month	Missing Day, Month, Year
Date of Last Therapy/Date of Initial Diagnosis	Assign 1	Assign January 1 if prior to date of informed consent, otherwise use date of informed consent	Missing (do not impute)
Adverse Event/Medication Start Date	Assign first day of month unless it is the month of first dose of study medication. Otherwise, assign date of first dose of study medication.	Assign January 1 unless the year is year of first dose of study medication. Otherwise, assign date of first dose of study medication.	Assign date first dose of study medication.
Adverse Event/Medication End Date	Assign the last day of the month or end of study date, whichever is earlier.	Assign December 31 or end of study date, whichever is earlier.	If ongoing, end date is missing. Otherwise, assign end of study date.

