### 6.3 Prior and Concomitant Medications and Procedures

Prior medications and procedures include any medication or non-drug therapy or procedure taken or performed within 30 days prior to screening and before the first dose of study drug. Prior medications will be coded using the World Health Organization Drug Dictionary [10].

Concomitant medications are all medications, other than the study drug, taken on or after the first day of study drug dose through 30 days after end of treatment. Concomitant medications and procedures will be coded using the World Health Organization Drug Dictionary.

Medications that started before the first dose of study drug and were ongoing on the date of the first dose will be considered concomitant medications.

The number and proportion of the subjects who took each medication, or had qualifying concomitant procedures, will be tabulated by the ATC-2 level and preferred name for concomitant medications. A subject will only be counted once within each ATC-2 code and within each preferred name.

Prior and concomitant medications will also be listed for ITT.

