## 9.0 SAFETY ANALYSIS

### 9.1 Adverse Events

Adverse events (AEs) will be coded using MedDRA v20 or later and will be classified by System Organ Class (SOC) and preferred term (PT).

Severity of AEs will be assessed according to CTCAE (v4.03).

Prior AEs are those occurring after subject sign off the informed consent and before the administration of the first dose of study treatment.

Drug-relatedness to the study drugs is captured in five categories as follows:

- Definitely related (The AE is clearly related to the investigational agent)

- Probably related (The AE is likely related to the investigational agent)
- Possibly related (The AE may be related to the investigational agent)
- Unlikely related (The AE is doubtfully related to the investigational agent)
- Unrelated (The AE is clearly not related to the investigational agent)

TEAEs are considered as related to the study drug if entered as definitely, probably or possibly related to study drug as assessed by the Investigator. If a subject has multiple occurrences of the same system organ class (SOC) or preferred term, then only the most severe event will be summarized in the tables for that SOC and preferred term.

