### 9.1.1 Treatment-Emergent Adverse Events

Treatment-emergent adverse events (TEAEs) are defined as any AEs that started after dosing or worsened in severity after dosing.

An overall AE summary for number of subjects will be presented for the following categories:

- Any Adverse Event
- Any TEAE
- Any Deaths within the AE reporting period
- Any study drug-related adverse event (TRAE) (i.e., related to durvalumab, tremelimumab and/or vaccine)
  - Any durvalumab related TRAE
  - Any tremelimumab related TRAE
  - Any vaccine related TRAE
- Any TEAE  $\geq$  CTCAE Grade 3
- Any TRAE  $\geq$  CTCAE Grade 3
- Any treatment-emergent Serious AEs (SAEs)
- Any Serious TRAEs
- Any TEAE leading to treatment (durvalumab, tremelimumab, and/or vaccine) discontinuation
  - Related to durvalumab
  - Related to tremelimumab
  - Related to vaccine

The following events will be tabulated by SOC and PT. Summaries will be sorted by decreasing frequency of PT within SOC which is sorted alphabetically.

- TEAEs by SOC and PT
- TEAEs by PT frequency only
- Treatment-emergent SAEs
- Treatment-related AEs
  - Durvalumab related
  - Tremelimumab related
  - Vaccine related
- Treatment-related SAEs
- TEAEs leading to treatment (durvalumab, tremelimumab, and/ or vaccine) discontinuation
  - Durvalumab discontinuation
  - Tremelimumab discontinuation
  - Vaccine discontinuation
- DLTs

A summary of TEAEs by SOC, PT and maximum severity, sorted by decreasing frequency of PT within SOC which is sorted alphabetically, will also be provided for:

- TEAEs
- TEAEs  $\geq$  CTCAE Grade 3
- Treatment related AEs
  - Durvalumab related
  - Tremelimumab related
  - Vaccine related
- TRAEs  $\geq$  CTCAE Grade 3

In tabulation by severity grade,

- For a given SOC, only the most severe SOC for each subject will be included.
- For a given PT, only the most severe PT for each subject will be included.

The following listings will be provided:

- All AEs (flag TEAE)

- DLTs
- SAEs
- TEAEs leading to study treatment discontinuation
- TEAEs leading to study drug (durvalumab or tremelimumab) dose modifications
- Deaths in the AE reporting period

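### The AE/medication start-date row of SAP Table 4 assigns the first-dose date without looking at the end date, so an AE that resolved in screening can be dated after its own end and tabulated as treatment-emergent.

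*SAP*

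**What the plan says.** SAP 11.1, Table 4, has one row for AE and medication start dates.

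- **Day missing:** "Assign first day of month unless it is the month of first dose of study medication", followed by "Otherwise, assign date of first dose of study medication".
- **Day and month missing:** "Assign January 1 unless the year is year of first dose of study medication", followed by the same first-dose instruction.
- **Whole date missing:** "Assign date first dose of study medication".

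The end-date row, when the day is missing, reads "Assign the last day of the month or end of study date, whichever is earlier". Neither row refers to the other, and I found no cross-check elsewhere in the SAP or protocol.

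The classifications that use these dates are as follows.

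- **TEAE (SAP 9.1.1):** "any AEs that started after dosing or worsened in severity after dosing".
- **Prior AE (SAP 9.1):** "Prior AEs are those occurring after subject sign off the informed consent and before the administration of the first dose of study treatment".
- **Concomitant medication (SAP 6.3):** "Concomitant medications are all medications, other than the study drug, taken on or after the first day of study drug dose", up to 30 days after the end of treatment. Drugs begun earlier and still ongoing at first dose also count.

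Protocol 7.1.5 requires AEs to be documented from consent. SAP 3.3, Table 1, puts screening at Day -28 to -1.

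**The concern.** Assigning first dose to an unknown start is a familiar conservative convention: when in doubt, count the event as on-treatment. It works when the end date is missing, the event is ongoing, or the end falls on or after first dose. When the end date is already known to precede first dose, there is no doubt about timing, and the rule replaces a consistent record with an impossible one.

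What is at stake is the content of the TEAE tables. Safety and tolerability is the primary objective in both phases (Protocol 4, SAP 2.1), and incidence by SOC, preferred term and maximum severity is its main display. The SAP keeps a separate class for events between consent and first dose. Table 4 can move an event out of that class.

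**Working it through.** The plan states no figure on this point, so there is none to reproduce. The check applies Table 4 literally.

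**Worked example.** Take first dose on 20 March 2019 and an AE with a known end on 12 March 2019.

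| Recorded start | Table 4 start | Start minus end |
|---|---|---|
| UNK-Mar-2019 | 20 Mar 2019 | +8 days |
| UNK-UNK-2019 | 20 Mar 2019 | +8 days |
| wholly missing | 20 Mar 2019 | +8 days |

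An imputed end date can give the same result. With the start wholly missing and the end recorded as UNK-Feb-2019, the end becomes 28 February 2019 and the start 20 March 2019, which is 20 days later.

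**Against the definitions.** An event that ended on 12 March occurred before the first dose, so it meets the prior-AE definition and cannot have started or worsened after dosing. Its imputed start of 20 March no longer precedes first dose, so a program that classifies on start date would take it out of the prior class.

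**Which branches cause it.** I took every first-dose date in 2019 (an arbitrary year) and every start/end pair lying wholly in the 28-day screening window, with a complete end date before first dose. Pairs per first-dose date: 28 × 29 / 2 = 406. Total: 406 × 365 = 148,190.

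| Missing part of start | Start after end | Share |
|---|---|---|
| Day | 55,622 / 148,190 | 37.5% |
| Day and month | 140,476 / 148,190 | 94.8% |
| Whole date | 148,190 / 148,190 | 100% |

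Every inversion came from the first-dose branch. The first-of-month branch (92,568 pairs) and the 1 January branch (7,714 pairs) produced none. The shares give equal weight to each date pair. They show where the rule fails and are not expected rates.

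**With an end-date condition.** Allowing first dose only when the end date does not precede it, and otherwise an earlier consistent date, reduces the inversions to 0 of 148,190 in all three rows. In the worked example, with consent assumed 28 days before first dose (20 February), the three starts become 1 March, 20 February and 20 February. All are before 12 March.

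**Size per subject.** The planned arm size is 20 (Protocol 3.1.6, SAP 2.5), so one subject is 1/20 = 5 percentage points of a row. SAP 9.1 and 11.2 count a subject once per SOC or preferred term. The shift therefore occurs only in a row where that subject is not already counted.

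**The case against.** The best defence is that little follows from this in practice. The event must begin and end in at most 28 days, with an incomplete start but an end date that is complete or still falls before first dose. Protocol 7.1.5 asks for onset and resolution dates for every AE. SAP 11.1 lists data as collected and the AE listing flags TEAEs, so a reader could spot an inversion. A careful programmer would also not let an imputed date override an observed one. This supports a low priority. It does not cure the rule, because listings do not correct the tables and the SAP does not instruct the programmer to make the check.

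A reader might also infer several stronger things that the documents do not support.

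- **That every partial start date is set to first dose.** Only the three cases above are; other partial dates go to the first of the month or 1 January.
- **That a drug stopped before Day 1 becomes concomitant.** SAP 6.3 asks when the drug was taken, or whether it was ongoing at first dose. A drug with a known earlier stop fails both tests, whatever start is imputed.
- **That the SAP states such an AE is a TEAE.** The definition says after dosing, and neither document says how an event dated on the first-dose day is treated. Counting it as a TEAE is the ordinary result but not a stated one.
- **That the overall any-TEAE rate moves by 5 points.** It moves only if the subject has no other TEAE. In the earlier trial of this vaccine (Protocol 1.2.3) all subjects reported at least one AE.
- **That DLTs, the RCD or treatment-related tables are affected.** These depend on assessed relatedness, and an event that resolved before any study drug should not be judged related.
- **That negative durations distort an analysis.** No AE or medication duration is summarised.

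**Conclusion.** The rule is wrong as written, and the consequence is minor. For an AE in one of the three first-dose cases whose known or imputed end date precedes first dose, Table 4 produces a start after the end, contradicts the prior-AE definition and would ordinarily place a pre-treatment event in the TEAE tables. For a medication in the same position the imputed start is equally impossible, but the record is still prior.

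In an arm of 20, each affected subject changes an SOC or preferred-term row by at most 5 points. The number of such records is not given in the documents and is probably small, given the short screening window. The conclusion assumes that Table 4 is programmed as written and that an AE dated on the first-dose day is tabulated as treatment-emergent.

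**What to change.** Add to the AE/medication start-date row of Table 4:

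*Use the first-dose date only if the end date is missing, ongoing, or on or after first dose. If the known or imputed end date is before first dose, impute the earliest date consistent with the known parts (for AEs, not before consent), not after the end date, and classify the record as prior.*

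Two edge cases should be settled at the same time. A medication with a wholly missing start has no lower bound, so its start can stay missing while the record is classed as prior. If the recorded parts of the start already contradict the end date, no imputation can satisfy both, and the record should be queried.

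The cost is a short addition to the SAP and one check in the program that derives the dates. No data collection changes.
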